8.2.4 Other Endpoints

Not applicable

PFIZER CONFIDENTIAL

9 APPENDIX

9.1 APPENDIX 1: Diagnosis and Procedure Codes used in the study

Variable	Code
Breast cancer	ICD9 174.x or 175.x or ICD10 C50.x

9.2 APPENDIX 2: Description of data elements used in the study

The following data elements will be extracted from feeds and/or curated by Certified Tumor Registrars (CTRs) for this study:

Data Elements	Description
Demographic characteristics	
Date of birth	Year, month, day (Availability of the exact date will depend on the Expert de-ID approach)
Date of initial BC diagnosis	Date of initial breast cancer (BC) diagnosis
Date of A/MBC diagnosis	Date of advanced/metastatic breast cancer (A/MBC) diagnosis
Patient sex	Male, Female, Transsexual, Other, Not Provided
Primary race	American Indian/Alaska Native; Asian; Black/African American/Native Hawaiian/Pacific Islander; White; Not Provided; Other (Exact list will depend on the expert de-ID approach)
Secondary race	(if provided) (Exact list will depend on the expert de-ID approach)
Ethnicity	Non-Hispanic/Non-Latino; Hispanic/Latino; Unknown (Exact list will depend on the expert de-ID approach)
Region of residence	Northeast, Midwest, South, West Captured at A/MBC diagnosis (Exact list will depend on the expert de-ID approach)
Insurance type	Medicare/Medicaid; Commercial; Commercial and Medicare/Medicaid; None; Not Provided Captured at 1) date of A/MBC diagnosis; and 2) at initiation of palbo
Menopause status	Premenopausal; Postmenopausal; Perimenopausal; Unknown; Not applicable. Captured on date closest to but before: 1) A/MBC diagnosis; and 2) initiation of palbo

PFIZER CONFIDENTIAL

	
Menopausal status: captured if explicitly stated in clinician notes. Otherwise captured based on following definition of menopause from NCCN Guideline v.3.2019:
 
Prior bilateral oophorectomy (date of surgery)
 
Age >=60 years old
 
Age <60 years old and amenorrheic for 12 months+ in the absence of chemotherapy, tamoxifen, toremifene, or ovarian suppression.
 
Additionally, type, name, and start/end date of ovarian suppression agent is captured

Date of death	If patient vital status = deceased, date of death from the medical record (capturing from EMR, registries, third party integrations) (Availability of the exact date will depend on the Expert de-ID approach)
Last contact date	If patient is alive (not deceased), date of the last contact by a healthcare provider from the medical record (Availability of the exact date will depend on the Expert de-ID approach)
Clinical characteristics	
Breast cancer histology	List captured at initial breast cancer diagnosis including: Adenoid cystic; Cribriform; Ductal; Inflammatory; Intraductal; Lobular; Medullary with lymphoid stroma; Medullary, NOS; Mucinous; Paget's disease and infiltrating; Paget's disease and intraductal; Papillary; Secretory; Squamous cell; Tubular, and more
ECOG/KPS performance score	Score captured on date closest to (with a ± 60 day cutoff around) 1) A/MBC diagnosis; and 2) initiation of palbo
Stage at initial BC diagnosis	0, I, IA, IB, II, IIA, IIB, III, IIIA, IIIB, IIIC, IV, Unable to stage, Not found, Not applicable
Presence of distant metastasis	
Yes; No
 
Note: this variable would be "yes" if patient is diagnosed with de novo metastatic breast cancer or if patient developed metastasis after initial breast cancer diagnosis

Date of first distant metastasis	Same as initial BC diagnosis if de novo metastatic BC, otherwise captured as date that the patient developed distant metastatic disease
Site(s) of distant metastasis at MBC diagnosis	
Bone; Chest Wall; Contralateral Breast; Distant Lymph node(s); Liver; Lung; Peritoneum; Pleural nodules; Malignant pleural effusion; Skin; Brain (brain and spinal metastases); Ovary; Undocumented; Other, Specify;
 
Visceral sites (Liver, Lung, Peritoneum and Pleural nodules);

PFIZER CONFIDENTIAL

	Bone only
Comorbidities	List of comorbidities at time of A/MBC diagnosis (sourced from problem list encompassing entire patient journey and confirmed from clinician notes), including: anemia, heart arrhythmia, hypertension, myocardial infarction, congestive heart failure, peripheral vascular disease, cerebrovascular accident, hemiplegia, chronic obstructive pulmonary disease, ulcer disease, diabetes with chronic complications, diabetes without chronic complications, renal disease, connective tissue disease such as rheumatoid arthritis or lupus, Alzheimer's or other dementia, cirrhosis or other serious liver disease, non-breast cancer malignancy (excluding sites of breast cancer metastasis and malignant neoplasm of skin), metastatic solid tumor (other than breast cancer), HIV/AIDS, and other comorbidities of interest
Note: comorbidities in bold are in CCI; CCI listed in derived variables section	
Biomarkers	
ER, PR, HER2 status	Positive; Negative; Equivocal; Unknown
ER, PR, HER2 test type	ISH, IHC, NGS, PCR, Other, Unknown
ER, PR, HER2 sample collection date	Year, month, day
ER, PR, HER2 report date	Year, month, day
BRCA status	BRCA1 Mutation; BRCA2 Mutation; BRCA NOS Mutation
BRCA sample collection date	Year, month, day
BRCA report date	Year, month, day
Treatment modalities prior to A/MBC diagnosis	
Breast surgery	Yes; No
Surgery type	Partial mastectomy; Lumpectomy / excisional biopsy; Segmental mastectomy; Subcutaneous mastectomy; Total mastectomy; Modified radical mastectomy; Radical mastectomy; Extended radical mastectomy; Mastectomy, NOS; Surgery, NOS
Note: if multiple, all will be listed (longitudinal data)	

PFIZER CONFIDENTIAL

Surgery date	Year, month, day
Breast radiation therapy	Yes; No
Radiation therapy site	Whole breast; Partial breast; Chest wall; Regional lymph nodes; Unknown Note: limited to primary breast cancer site. If multiple, all will be listed (longitudinal data)
Radiation start/end dates	Year, month, day
Chemotherapy	Yes; No
Recurrence	
Patient had recurrence	Yes; No
Recurrence date	Year, month, day (Captures first time locally, first time regionally, and first time distant; if multiple sites, hierarchy prioritizes most advanced site)
Recurrence site	Local; Regional; Distant; Unknown
Recurrence test source	Biopsy; Imaging; Imaging confirmed by biopsy; Unknown
Clinician confirmation of recurrence	Sources including: Medical oncology consult/note; Radiation oncology note; Discharge summary; Other
Recurrence linked to therapy	Yes; No
Progression	
Patient had progression	Yes; No
Progression date	Year, month, day
Progression test source	Biopsy; Imaging; Imaging confirmed by biopsy; Unknown
Clinician confirmation of progression	Sources including: Medical oncology consult/note; Radiation oncology note; Discharge summary; Other
Clinician confirmation date	Year, month, day

[figure not shown]
PFIZER CONFIDENTIAL

Progression linked to therapy	Yes; No
Complete systemic therapy history	
Therapy name	Therapy name
Administration route	Categories including: Oral; Infusion; Injection; Other; Unknown
Therapy start date	Year, month, day
Therapy end date	Year, month, day
Start reason	Recurrence; Progression; Other reason not related to worsening disease
Start reason source date	Year, month, day (can be linked to clinician confirmation date of recurrence/progression if start reason is recurrence/progression)
Stop reason	Categories including: Progression; Toxicity; End of planned therapy; Insurance changes; Treatment ongoing; Other
Stop reason source date	Year, month, day (can be linked to clinician confirmation date of recurrence/progression if stop reason is recurrence/progression)
Treatment part of clinical trial	Yes; No
Palbociclib-specific variables (captured in addition to above variables)	
Combination AI partner	Letrozole, Anastrozole, Exemestane
Concomitant LHRH Agonists	Goserelin (Zoladex), Histrelin (Vantas), Leuprolide (Eligard, Lupron), Triptorelin (Trelstar)
Dose 1 (start dose)	125mg, 100mg, 75mg
Dose 1 start date	Year, month, day
Dose n (where n>=2)	125mg, 100mg, 75mg
Dose n start date	Year, month, day
Dose n adjustment type or reason	Categories include schedule change; dose delay; hold; cost; patient refusal; toxicity

Variables that will be derived from curated data will include the following:

Data Elements	Description
-----------------------------	---------------------------

PFIZER CONFIDENTIAL

Age at A/MBC diagnosis	Age in years; age categories: <50, 50-64, 65 –74, ≥75 years (Exact list will depend on the expert de-ID approach)
Age at start of palbociclib treatment	Age in years; age categories: <50, 50-64, 65 –74, ≥75 years
Date of death	If patient vital status = deceased, date of death from the medical record (capturing from EMR, registries, third party integrations) (Availability of the exact date will depend on the Expert de-ID approach)
Palbo dose change ever	Yes; No
Disease Free Interval (DFI)	Months from the end of adjuvant therapy to the date of disease recurrence ≤12 months, 13-24 months, 25-36 months >36 months Unknown
Endocrine sensitivity	≥12 months without recurrence/progression after completion of endocrine therapy in the adjuvant setting
Primary endocrine resistance	Relapse during first 2 years of adjuvant endocrine therapy or progressive disease within first 6 months of first-line endocrine therapy for metastatic breast cancer
Secondary endocrine resistance	Relapse while on adjuvant endocrine therapy but after first 2 years of treatment, relapse within 12 months of completing adjuvant endocrine therapy, or progressive disease 6 or more months after starting endocrine therapy for metastatic breast cancer
Charlson Comorbidity Index (CCI)	Calculated based on the presence of 17 Charlson comorbidities at A/MBC
Line of therapy	Line number (1; 2; 3; etc.) in the A/MBC setting assigned based on Syapse line of therapy algorithm
Regimen medication(s)	Systemic therapies included in line regimen defined by Syapse line of therapy algorithm
Line start date	Year, month, day
Line end date	Year, month, day
Time to first dose change	Days from palbo dose 1 start date to palbo dose 2 start date, if applicable
Number of dose changes	Number of dose reduction(s) and number of dose increases over the calendar time (quarter since February 2015) and over treatment cycle since palbo dose 1 start date

PFIZER CONFIDENTIAL

Bone only distant metastasis at MBC diagnosis	From sites of distant metastasis: bone only
Visceral distant metastasis at MBC diagnosis	From sites of distant metastasis: visceral sites Visceral sites defined as: Liver; Lung; Peritoneum; Pleural nodules; Malignant pleural effusion
Disease burden at MBC diagnosis	Lesions in liver, bone, or lung metastatic sites: Single, Multiple, Unknown
Effectiveness Outcomes	
Real-world Overall Survival (rwOS)	Length of time from the start of palbociclib + AI treatment to the earliest of the following: date of death, date of last contact, or the end of study period
Real-world progression free survival (rwPFS)	Length of time from the start of palbociclib + AI treatment to the earliest of the following: clinician-assessed progression event, date of death, date of last contact, or end of study period. Progression identified from tissue/pathology or imaging/radiology and confirmed by clinician (in 2 separate data points), from MA guidance: 
1. Medical Oncology Consult/Note (can also include medical oncologist history and physical (H&P))2. Radiation Oncology note/consult/(can also include radiation oncology H&P)3. Progress Note (can also include /H&P/Consult - use this option for physician of other discipline in the absence of numbers 1 and 2)4. Discharge Summary5. Nursing Note6. Care Everywhere/Scanned Documents/External lab reports (for information diagnosed outside of facility for which patient is being abstracted)7. Other
Real world time to treatment discontinuation (rwTTD)	Length of time from the start of palbociclib + AI treatment to the earliest of the following: date the patient discontinues first-line treatment, date of death, last known usage of first-line treatment, or end of study period
Real world time to next treatment (rwTTNT)	Length of time from the start of palbociclib + AI treatment to the earliest of the following: subsequent line of therapy initiation, date of death, date of last contact, or end of the study period

Real world time to dose adjustment (rwTTDA)	Length of time from the start of palbociclib + AI treatment to the earliest of the following: date of first-line treatment dose adjustment, date of death, last known usage of first-line treatment, or end of study period.
Real world time to chemotherapy (rwTTC)	Length of time from the start of palbociclib + AI treatment to the earliest of the following: the day before the start of subsequent chemotherapy for patients with evidence of chemotherapy, or date of death for any reason. Or, where censored, the latest of date of last contact, or end of the study period.

PFIZER CONFIDENTIAL

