5 ENDPOINTS AND COVARIATES

Primary Endpoints-

1. To summarize the demographic and clinical characteristics.
Demographic characteristics will include

PFIZER CONFIDENTIAL

- Year of initial, metastatic and AMBC diagnoses;
- age at initial diagnosis, A/MBC diagnosis, start of palbociclib treatment and death;
- sex;
- race;
- ethnicity
- insurance status;
- menopausal status;
- region of residence at A/MBC diagnosis.

Clinical characteristics will include

[figure not shown]
- stage of initial diagnosis;
- histology;
- Eastern Cooperative Oncology Group (ECOG) performance status (where ECOG score unavailable, Karnofsky performance status will be converted to corresponding ECOG score);
- prior surgery (and type);
- prior radiation therapy (and type);
- comorbid disease burden (see Section 9.2);
- Charlson comorbidity index
- Sites of metastasis – visceral (liver, lung, peritoneum and pleural nodules), non-visceral, bone only
- Number of metastatic sites
 - Number of lesions in the site
 - Disease burden in the liver, lungs, bone
- time to metastasis (time between initial and metastatic diagnoses)
- HER2 and estrogen receptor (ER)/ progesterone receptor (PR) status;
- BRCA status
- modalities of treatment received prior to A/MBC diagnosis (chemotherapy, hormone therapy, surgery, radiation therapy);
 - Documentation of endocrine sensitivity and endocrine resistance if hormone therapy received in adjuvant setting
- disease free interval (time between completion of adjuvant therapy and diagnosis of A/MBC).

2. To summarize treatment patterns.

Treatment patterns will be evaluated by the review of

- the distribution of regimens;
- sequence of regimens across the lines;
- description of dosing which will include the starting dose, end dose, dose adjustment (dose increase and dose reduction), type of dose adjustment (dose modification, schedule changes, dose delay or hold), discontinuation reason (including death, progression, end of planned therapy, insurance changes, schedule change, dose delay, hold, cost, patient refusal, toxicity), and time to dose adjustment

PFIZER CONFIDENTIAL

[figure not shown]

3. To summarize the effectiveness outcomes of treatment-
 - a. Real-world progression-free survival (rwPFS) for the first-line therapy at time points 3, 6, 12, 18, 24, 30, and 36 months;
 - b. Real-world overall survival (rwOS) from the start of the first-line therapy at time points 6, 12, 18, 24, 30, and 36 months.

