7 STATISTICAL METHODOLOGY AND STATISTICAL ANALYSES

7.1 Statistical methods

Descriptive analyses: For categorical variables (eg region, race, and stage at initial diagnosis), data will include the frequency (number of cases) and percentage (%) of total patients observed in each category; for continuous variables (eg age and time from initial breast cancer diagnosis to metastatic diagnosis), variables will be presented as the mean, standard deviation (SD), median, 25th and 75th percentiles and ranges (minimum and maximum) in some cases. The calculation of percentages will always include the missing category in the case of missing values. Continuous variables may be categorized into intervals, with the distribution of patients (N, %) provided.

Kaplan-Meier curves and landmark analyses will be performed to estimate rwPFS, rwOS, rwTTD, rwTTC, rwTTDA and rwTTNT. Specifically, landmark time points are; 3, 6, 12, 18, 24, 30, and 36 months for rwPFS and 6, 12, 18, 24, 30, and 36 months for rwOS. For rwTTD and rwTTNT, landmark time points are; 3, 6, 12, 18, 24, 30, and 36 months. Ninety-five percent confidence intervals on the median rwPFS, rwOS, rwTTD, rwTTNT, rwTTC and rwTTDA will be reported.

Cox proportional hazard models may include age categories, race, ECOG performance, menopausal status, stage at initial diagnosis, time from initial diagnosis to metastatic diagnosis, metastatic status (De novo, versus number of metastatic sites), number of disease sites (1, 2, ≥ 3), prior endocrine therapy, prior chemotherapy, prior surgery, prior radiation therapy, bone-only disease, presence of visceral disease, and presence of brain metastases as appropriate based on availabilities of the data and sample sizes. Potential interactions may be examined using survival trees for time to events.

All data analysis will be executed using statistical software R version 3.6.1 or later.

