Kaplan-Meier survival analysis is used to descriptively characterize time to event outcomes. In this study, following time to event outcomes will be analyzed-

- Time to Real-world overall survival (rwOS)

[figure not shown]
The time origin for analysis of rwOS is start of the first-line therapy, and the terminal event is death. For patients not known to be deceased at the time of analysis, rwOS will be censored at the earliest of the last date of last contact or the end of the study period.

- Time to Real-world progression-free survival (rwPFS)

The time origin for analysis of rwPFS is start of the first-line therapy. Patients without a clinician-assessed progression event or death will be censored at the earliest of the following events: date of initiation of the 2nd line for patients with >1 line of therapy, date of last contact, or end of study period.

- Real world time to treatment discontinuation (rwTTD)

PFIZER CONFIDENTIAL

The time origin for analysis of rwTTD is start of the first-line therapy. Patients without first-line treatment discontinuation and who did not die will be censored at the earliest of the following events: last known usage of first-line treatment, or end of study period.

- Real world time to next treatment (rwTTNT)

The time origin for analysis of rwTTNT is start of the first-line therapy. Patients without a subsequent line of therapy initiation and who did not die will be censored at the earliest of the following events: date of last contact, or end of the study period.

- Real world time to chemotherapy (rwTTC)

The time origin for analysis of rwTTC is start of the first-line therapy. Patients who did not receive subsequent chemotherapy and who did not die will be censored at the latest of the following events: date of last contact, or end of the study period.

- Real world time to dose adjustment (rwTTDA)

The time origin for analysis of rwTTDA is start of the first-line therapy. Patients without a first-line treatment dose adjustment will be censored at the earliest of the following events: first-line treatment discontinuation, date of death, date of last contact, or end of the study period.

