One Kaplan-Meier analysis is generated for each time to event endpoint. Kaplan-Meier analysis will include number of patients with events and censored patients, median, 25th percentile and 75th percentile times to event (in months), 95% CI of the quartiles and ranges (minimum and maximum). Kaplan-Meier analysis will be repeated in the subgroup of patients who received a starting dose of 125mg.

One Cox regression analysis will be generated for each time to event endpoint, provided the sample size supports the analysis. Demographic and baseline clinical characteristics, some examples are detailed in section 7.1, will be included to the extent that sample size permits. Results from this analysis results will include parameter estimates, p-values, standard errors, hazard ratios and 95 % CIs of hazard ratios. The proportional hazards assumption will be assessed graphically with the inspection of Schoenfeld residuals and by including interaction terms between the variables and log(time).

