Variable/Statistic	palbociclib + AI (n=xxx)
Perimenopausal	n (x.x%)
Unknown	n (x.x%)
Not applicable	n (x.x%)
Region of Residence at A/MBC diagnosis, n (%)	
Northeast	n (x.x%)
Midwest	n (x.x%)
South	n (x.x%)
West	n (x.x%)

PFIZER CONFIDENTIAL

Clinical Characteristics and Comorbidities

Table 15.1.3. Clinical Characteristics and Comorbidities

Variable/Statistic	palbociclib + AI (n=xxx)
Stage at Initial Breast Cancer Diagnosis, n (%)	
Stage 0	n (x.x%)
Stage I	n (x.x%)
Stage IA	n (x.x%)
Stage IB	n (x.x%)
Stage II	n (x.x%)
Stage IIA	n (x.x%)
Stage IIB	n (x.x%)
Stage III	n (x.x%)
Stage IIIA	n (x.x%)
Stage IIIB	n (x.x%)
Stage IIIC	n (x.x%)
Stage IV	n (x.x%)
Unable to stage	n (x.x%)
Not found	n (x.x%)
Not Applicable	n (x.x%)
Histology, n (%)	
Adenoid cystic	n (x.x%)
Cribiform	n (x.x%)
Ductal	n (x.x%)
Inflammatory	n (x.x%)
Intraductal	n (x.x%)
Lobular	n (x.x%)
Medullary with lymphoid stroma	n (x.x%)
Medullary	n (x.x%)
NOS	n (x.x%)
Mucinous	n (x.x%)
Paget's disease and infiltrating	n (x.x%)
Paget's disease and intraductal	n (x.x%)
Papillary	n (x.x%)
Secretory	n (x.x%)
Squamous cell	n (x.x%)
Tubular	n (x.x%)
Performance Status at A/MBC diagnosis (ECOG Score), n (%)	
Sub-total	n (x.x%)
0	n (x.x%)
1	n (x.x%)
2	n (x.x%)
3	n (x.x%)
4	n (x.x%)
Undocumented	n (x.x%)
Total comorbidities, n (%)	
0	n (x.x%)
1	n (x.x%)
2	n (x.x%)
≥3	n (x.x%)
Charlson Comorbidity Index (CCI), n (%)	
0	n (x.x%)
1	n (x.x%)
2	n (x.x%)

PFIZER CONFIDENTIAL

Table 15.1.3. Clinical Characteristics and Comorbidities

Variable/Statistic	palbociclib + AI (n=xxx)
3	n (x.x%)
≥4	n (x.x%)
Time to Metastasis, n (%)	
≤12 months	n (x.x%)
13-24 months	n (x.x%)
25-36 months	n (x.x%)
>36 months	n (x.x%)
De novo metastatic	n (x.x%)
Disease free Interval, n (%)	
≤12 months	n (x.x%)
13-24 months	n (x.x%)
25-36 months	n (x.x%)
>36 months	n (x.x%)
De novo metastatic	n (x.x%)
Disease Free Interval (months)	
n	xx
Mean (SD)	x.x (x.xx)
Median (Q1, Q3)	x.x (x.x, x.x)
Min, Max	x.x, x.x
Metastatic Group, n (%)	
De novo	n (x.x%)
Recurrent	n (x.x%)

Table 15.1.4 Comorbidities Occurring in at Least 5% of Patients

Variable, n (%)	palbociclib + AI (n=xxx)
XXX	n (x.x%)

Comorbidities presented in descending order of frequency

PFIZER CONFIDENTIAL

Table 15.1.5. Summary of Sites of distant metastasis and disease burden at A/MBC diagnosis

Variable, n (%)	palbociclib + AI (n=xxx)
Number of distant metastatic sites	
1	n (x.x%)
2	n (x.x%)
≥3	n (x.x%)
Sites of distant metastasis: bone only	
Yes	n (x.x%)
No	n (x.x%)

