8.2 Objective 2: Effectiveness Outcomes

8.2.1 Endpoint Data

Real world Overall Survival

Table 15.2.1.19. Kaplan-Meier Analysis of rwOS from Start of 1L Using Regimen-Based Lines of Therapy

OS	palbociclib + AI (n=xxx)
No. of Events/No. of Patients	xxx/xxx
No. of Censored	xx
Minimum, Maximum	xx.x, xx.X
Kaplan-Meier Estimates in months (95% CI)	
25 th percentile	xx.x (xx.x, x,x)
Median	xx.x (xx.x, x,x)
75 th percentile	xx.x (xx.x, x,x)

Figure 15.2.1.2. Kaplan-Meier Analysis of rwOS

Table 15.2.1.3. Cox Model for Assessing Factors Associated with rwOS from Start of 1L

Parameters	Estimate	Std Error	HR	95% CI for HR	P-Value
Age in years (≥ 75 vs <50)	x.xxx	x.xxx	x.xxx	x.xxx-x.xxx	x.xxxx
Age in years (65-74 vs <50)	x.xxx	x.xxx	x.xxx	x.xxx-x.xxx	x.xxxx
Age in years (50-64 vs <50)	x.xxx	x.xxx	x.xxx	x.xxx-x.xxx	x.xxxx
Race (Black or African American vs White)	x.xxx	x.xxx	x.xxx	x.xxx-x.xxx	x.xxxx
Race (Other vs White)	x.xxx	x.xxx	x.xxx	x.xxx-x.xxx	x.xxxx
ECOG/KPS (≥ 2 vs 0)	x.xxx	x.xxx	x.xxx	x.xxx-x.xxx	x.xxxx
ECOG/ KPS (1 vs 0)	x.xxx	x.xxx	x.xxx	x.xxx-x.xxx	x.xxxx
Menopausal status (post vs pre or peri)	x.xxx	x.xxx	x.xxx	x.xxx-x.xxx	x.xxxx
Metastatic group (de novo vs recurrent)	x.xxx	x.xxx	x.xxx	x.xxx-x.xxx	x.xxxx
Stage at Diagnosis (IV vs 0 or I)	x.xxx	x.xxx	x.xxx	x.xxx-x.xxx	x.xxxx
Stage at Diagnosis (III vs 0 or I)	x.xxx	x.xxx	x.xxx	x.xxx-x.xxx	x.xxxx
Stage at Diagnosis (II vs 0 or I)	x.xxx	x.xxx	x.xxx	x.xxx-x.xxx	x.xxxx

PFIZER CONFIDENTIAL

Table 15.2.1.3. Cox Model for Assessing Factors Associated with rwOS from Start of 1L

Parameters	Estimate	Std Error	HR	95% CI for HR	P-Value
Number of disease sites (≥ 3 vs 1)	x.XXX	x.XXX	x.XXX	x.XXX-x.XXX	x.XXXX
Number of disease sites (2 vs 1)	x.XXX	x.XXX	x.XXX	x.XXX-x.XXX	x.XXXX
Time from initial diagnosis to metastasis (≤ 36 vs > 36 months)	x.XXX	x.XXX	x.XXX	x.XXX-x.XXX	x.XXXX
Visceral disease (Yes vs No)	x.XXX	x.XXX	x.XXX	x.XXX-x.XXX	x.XXXX
Prior endocrine therapy (Yes vs No)	x.XXX	x.XXX	x.XXX	x.XXX-x.XXX	x.XXXX
Prior chemotherapy (Yes vs No)	x.XXX	x.XXX	x.XXX	x.XXX-x.XXX	x.XXXX
Prior surgery (Yes vs No)	x.XXX	x.XXX	x.XXX	x.XXX-x.XXX	x.XXXX
Prior radiation therapy (Yes vs No)	x.XXX	x.XXX	x.XXX	x.XXX-x.XXX	x.XXXX

Table 15.2.1.4. Kaplan-Meier Analysis of rwOS from Start of 1L Using Regimen-Based Lines of Therapy for Patients who Received 125mg Starting Dose**Figure 15.2.1.5. Kaplan-Meier Analysis of rwOS for Patients who Received 125mg Starting Dose**

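### The ECOG/KPS capture rule lets a score taken up to 60 days after palbociclib start displace a pre-treatment score, and the SAP does not say which captured score enters the Cox models as baseline

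*SAP*

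**What the plan says.** Section 9.2 (Appendix 2) gives the capture rule for ECOG/KPS: "Score captured on date closest to (with a ± 60 day cutoff around) 1) A/MBC diagnosis; and 2) initiation of palbo". This produces two scores per patient, each the nearest in time to its anchor, on either side of it. No preference for an earlier score and no tie rule is given.

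The same appendix treats menopausal status differently, at the same two anchors: "Captured on date closest to but before: 1) A/MBC diagnosis; and 2) initiation of palbo".

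On the use of ECOG:

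- Section 7.1 lists it as a candidate covariate: "Cox proportional hazard models may include age categories, race, ECOG performance, menopausal status, stage at initial diagnosis".
- Section 7.2 describes the covariates as baseline: "Demographic and baseline clinical characteristics, some examples are detailed in section 7.1, will be included to the extent that sample size permits".
- The Cox shell (Table 15.2.1.3) has two ECOG/KPS contrasts, 2 or more versus 0 and 1 versus 0. Neither states an anchor date.
- The descriptive shell (Table 15.1.3) reports only the diagnosis-anchored score: "Performance Status at A/MBC diagnosis (ECOG Score), n".

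Time zero is treatment start, not diagnosis. For overall survival, "The time origin for analysis of rwOS is start of the first-line therapy, and the terminal event is death". Section 7.2 sets the same origin for the other five endpoints.

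**The concern.** A baseline covariate in a Cox model should be known at time zero. Under the written rule a score recorded after treatment has begun can be taken even when a pre-treatment score exists. That later score may already carry the effect of early toxicity, early progression or early response. It can exist only for a patient who was alive and in contact on that date.

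For some endpoints the score could follow the event it is meant to help explain. A dose adjustment, or discontinuation of first-line treatment, may fall in the first 60 days. Appendix 2 lists toxicity, hold and dose delay among the dose-adjustment types or reasons. An ECOG score recorded after such an event, and perhaps because of it, could then serve as a baseline predictor of it.

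The hazard ratio for ECOG, and the adjustment of the other factors for ECOG, are at stake wherever ECOG is included. Separately, because two scores are captured and neither is assigned to the models, two programmers working from this text could fit different models.

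**Working it through.** The SAP states no figure on this point, so there is none to reproduce. The check applies the written rule and follows its consequences.

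**1. The rule applied to pairs of dates.** Inputs: the nearest-date rule and the 60-day limit, both from Appendix 2. The date pairs are illustrative. Day 0 is palbociclib start, and the score chosen is the one with the smallest |day| not above 60.

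| Scores available (day) | Chosen as written | Last score on or before day 0 |
|---|---|---|
| -20 and +10 | +10 | -20 |
| -30 and +28 | +28 | -30 |
| -45 and +14 | +14 | -45 |
| -7 and +28 | -7 | -7 |
| -14 and +14 | tie, no rule given | -14 |

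In the first three rows a pre-treatment score is available and is passed over.

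**2. How late the score can be.** 60 / 30.4375 = 1.97 months after time zero. The first landmark in Section 5 is at 3 months ("Real-world progression-free survival (rwPFS) for the first-line therapy at time points 3, 6, 12, 18, 24, 30, and 36 months"). 1.97 / 3 = 0.66, so the score can come from about two-thirds of the way to that landmark.

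**3. Whether the diagnosis anchor avoids the problem.** If palbociclib starts g days after A/MBC diagnosis, the diagnosis window ends 60 - g days after palbociclib start:

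- g = 14: 46 days
- g = 30: 30 days
- g = 45: 15 days
- g = 60: 0 days

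So it avoids the problem only when g is 60 or more. For smaller g a post-start score is taken only if no score lies nearer to diagnosis, so this route is narrower than the palbociclib-start anchor but still open.

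**4. How often a post-start score would be chosen.** The SAP gives no visit timing, so this rests on assumption. Take patients with a score on both sides of palbociclib start. Let the last pre-start score fall uniformly 0 to P days before start and the first post-start score uniformly 0 to Q days after. The share for whom the post-start score is nearer is P/(2Q) if P ≤ Q, and 1 - Q/(2P) if P > Q.

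- P = 7, Q = 60: 7/120 = 0.058
- P = 30, Q = 28: 1 - 28/60 = 0.533
- P = 60, Q = 14: 1 - 14/120 = 0.883

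With P from 7 to 60 and Q from 14 to 60, the share runs from about 6% to 88%. The documents do not narrow this range.

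**5. Effect on the hazard ratio.** Simulated Cox fits for rwPFS used inputs that are all assumed: median 22 months, 15% with ECOG 2 or more, 20-50% of scores taken after start, and censoring uniform over 6 to 60 months.

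- If 30-50% of patients with a post-start score who progress within 4 months have already worsened when scored, a true hazard ratio of 1.0 reads 1.07-1.31.
- If the score must precede progression and only progression within 2 months counts, it reads about 1.02-1.08.

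The result depends on the inputs. Neither setting allows for scores that improve on treatment.

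**The case against.** The strongest reply is that the SAP permits this but does not make it certain. Two scores are captured, and the only one tabulated is anchored at diagnosis. If that is also the score modelled, a post-start value enters only when treatment begins within 60 days of diagnosis and no score lies nearer to diagnosis. ECOG is also only a possible covariate, subject to sample size, in a descriptive study with no hypotheses. The menopausal-status rule concerns a different variable and does not by itself prove the ECOG rule wrong.

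All of this is fair, and it limits the consequence. It does not remove the problem. No section restricts ECOG to pre-start scores, both anchors allow a later one, and the modelled score is not named. The menopausal-status rule shows only that the SAP already has a before-the-anchor wording to draw on.

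A reader might infer that the rule inflates the ECOG hazard ratio by a known amount and shifts the other coefficients in all six models. The documents do not support that. They give no frequency of post-start scores and no rate of early deterioration, and a post-start score may also reflect response. The simulations describe one endpoint under assumed inputs, and the effect on other coefficients was not computed.

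It is also tempting to say that the correction needs no new data. Appendix 2 says that multiple entries are all listed for surgery and radiation, but not for ECOG, and it lists no ECOG date element. If only the nearest score was abstracted, the earlier one may not be held.

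**Conclusion.** The point stands as a defect in a stated rule together with an unnamed choice. As written, a score from up to 60 days after time zero can replace an available pre-treatment score and be modelled as baseline, and the SAP does not say which of the two captured scores the models use. The ECOG hazard ratio and the adjustment for ECOG may be biased. The size and direction cannot be derived from the SAP. The 6% to 88% share and the simulated hazard ratios are conditional illustrations, not estimates for this cohort. The effect is confined to Cox models that include ECOG, and every Kaplan-Meier curve, median and landmark estimate is unaffected. The change is worth making before the Cox results are relied on.

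**What to change.** 1. In Appendix 2, define baseline ECOG/KPS for the Cox models as the last score on or before palbociclib start within 60 days. Use a post-start score within the same window only if no earlier one exists, and flag it. Relative to the palbociclib-start capture this adds no missing values, because every patient with a score in the window keeps one.
2. In Section 7.1 and the Cox shells, name this value as the ECOG covariate.
3. Add it to Table 15.1.3 beside the score at A/MBC diagnosis, with the number flagged.
4. Repeat the Cox models with flagged scores set to not documented. The present shell has no row for undocumented ECOG, so state whether these patients form a category or drop out of that fit.

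The cost is a little extra programming. If only the single closest score was kept, or no score date, the affected charts also need rechecking.
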